Participants will attend an orientation session via Zoom or in person to introduce them to mindfulness, smoking cessation, and what is covered in the group sessions. This orientation will last 60-90 minutes. They will receive twice weekly group sessions (eight total during 4 weeks) via Zoom or in person that were manualized and will be delivered in Spanish or English by a Hispanic instructor(s) experienced in MT (a single therapist with >4 years of training in MT). We will e-mail participants study materials ahead of the first group session, such as the participant study booklet. We will also communicate with participants using WhatsApp to send them reminders and links to mindfulness recordings.

The overarching theme of momentary awareness and acceptance of cravings and affect (e.g., stress, anxiety etc.) will be introduced and reinforced in complementary ways throughout the training. Each session will last 45-60 minutes.

- a. *Session (1):* Will introduce participants to the concept of how smoking can become a habituated behavior triggered by an environmental, physical, or mental stimulus through associative learning. It also will explore how cravings feel in the body and how MT can help individuals become more aware of these processes.
- b. *Session (2):* Will examine how thoughts, emotions and body sensations become triggers for craving and smoking and introduce a technique to ‘mindfully’ work with cravings (Recognize, Accept, Investigate and Note what cravings feel like as they arise; acronym: RAIN).
- c. *Session (3):* Will introduce how difficult emotions perpetuate smoking as well as a standard meditation technique called loving-kindness as a way to work with them. Loving-kindness is practiced through directed well wishing, typically by repetition of phrases such as ‘may X be happy.’
- d. *Session (4) (quit date):* Will teach participants how cravings thwart long-term goals, and reinforce mindfulness techniques as a way to help individuals disengage from habitual responding and realign with their goals.
- e. *Session (5):* Will introduce participants to mindfulness practice in everyday life, including “awareness of breath” meditation and mindful walking (“four modes of walking”), during which individuals practice systematically noting

objects that they see, and then objects that they hear, then objects that they smell, and then tactile objects such as the pressure of their feet on the ground).

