- f. *Session (6):* Will explore the automaticity of thought, and how thoughts can lead to habitual behaviors.
- g. *Session (7):* Will reinforce the concept of acceptance and its role in changing habits. It will also explore how both mental and physical actions can “plant seeds” for future actions and habits.
- h. *Session (8):* Will summarize the course tools and explore ways of maintaining these in the future. Home practice will be suggested after each session as a combination of formal MT meditations (the “body scan” which teaches individuals to systematically pay attention to different parts of their bodies as a way to reduce habitual mind-wandering and strengthen their attentional capacities, loving-kindness, and awareness of breath, which through focused attention on the breath also is intended to help individuals retrain their minds from habitually engaging in self-related pre-occupations -such as thinking about the past or future, or reacting to stressful stimuli- to more present moment awareness), and informal practices (four modes of walking, mindfulness of daily activities, mindfulness of smoking, RAIN). Participant will receive meditation recordings to practice.

[figure not shown]
Participants will receive a weekly phone call to ask a few questions on their use of the mindfulness practices taught in the sessions. This will take about 5 minutes.

Participants will receive \$20 for completing the baseline assessment, \$10 for attending each of the 8 sessions, \$10 for the end of the treatment assessment, and \$25 for the 3-month follow up assessment (a total of \$135).

Arm 2: Contingency Management (CM) Smoking Cessation Intervention

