- *Demographics and HIV history:* Age, race/ethnicity, birth origin, years in USA, relationship status, education, employment, income, acculturation, discrimination, self-identity, time since HIV diagnosis, HIV treatment.

Smoking status will be verified using breath carbon monoxide (CO [< 8 parts per million (ppm)], which can be determined quickly through a small, hand-held monitor and/or using a saliva screening test (cutoff concentration of ≤ 30 ng/mL), which can be determined quickly through a NicoTests saliva sample.

- *Smoking:* Smoking history, past quit attempt, motivation to quit, confidence in quitting, Fagerström test for nicotine dependence,^[15] 12-item smoking self-efficacy to resist urge to smoke,^[16] and 15-item Minnesota nicotine withdrawal scale (i.e., craving, irritability, anxiety, depression).^[17]

- *Mindfulness skills:* The 15-item short form five facets of mindfulness questionnaire that measures MT skills related to observing, describing, acting with awareness, non-judging of inner experience, and non-reactivity to inner experience.^[18]

- *Others:* The 20-item Centers for the Epidemiologic Study of Depression (CES-D) scale,^[19] social support,^[20] quality of life,^[21] and alcohol and substance use (ASSIST).^[22]

2. End-of treatment assessment (one month after quit date):

- The follow up assessment will occur at 1 months after quit date. The visit will last approximately 45 minutes.

- Information on number of sessions that was attended.

- *Acceptability:* The acceptability will be assessed by 3 items “How satisfied were you with the intervention?”, “How likely are you to recommend this intervention to a friend?” and “How useful was the intervention?”

Smoking Cessation: Main smoking cessation outcome is 7-day point-prevalence abstinence (defined as self-report of not smoking in the past 7-days; not even a puff) and confirmed smoking cessation by expired carbon monoxide (CO) level cutoff of < 8 ppm using a coVita iCO™ Smokerlyzer® and/or NicoTests saliva sample of ≤ 30 ng/mL at the 1-month follow up. Secondary outcomes include the reduction in number of cigarettes smoked per day.^[23,24] Relapse is defined as smoking at least once/week on two consecutive weeks.^[25] These are described in more detail below.

3. Three-month Follow-up Assessment (3-month after quit date):

- The follow up assessment will occur at 3 months (+30 days) after quit date. The visit will last approximately 45 minutes.

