- All baseline assessment will be re-administered except demographics.

- Information on number of sessions that was attended.
- *Acceptability:* The acceptability will be assessed by 3 items “How satisfied were you with the intervention?”, “How likely are you to recommend this intervention to a friend?” and “How useful was the intervention?”
- *Smoking Cessation:* Main smoking cessation outcome is 7-day point-prevalence abstinence (defined as self-report of not smoking in the past 7-days; not even a puff) and confirmed smoking cessation by expired carbon monoxide (CO) level cutoff of < 8 ppm using a coVita iCO™ Smokerlyzer® and/or NicoTests saliva sample of ≤ 30 ng/mL at the 3-month follow up. Secondary outcomes include the reduction in number of cigarettes smoked per day.[23,24] Relapse is defined as smoking at least once/week on two consecutive weeks.[25] These are described in more detail below.
- *Process evaluation:* Semi-structured post-intervention evaluation interviews will be conducted with randomly selected participants to further inform our assessment of acceptability and perceived helpfulness of interventions, and identifying key areas for refining the intervention protocols (e.g., improving access, content, usability). These will be conducted in-person or via Zoom and participants will receive \$25 for completing the interview.

Primary Outcome Measure Title: Smoking cessation - 7-day point-prevalence abstinence.

Outcome Measure Description:

Defined as self-report of not smoking in the past 7-days, not even a puff and confirmed by expired carbon monoxide (CO) level cutoff of < 8 ppm using a coVita iCO™ Smokerlyzer® and/or NicoTests saliva sample of ≤ 30 ng/mL.

Outcome Measure Timeframe:

4 weeks (end of treatment), and 3 months

Secondary Outcomes

1. Treatment-specific retention rates for study measures.
 - Defined as: Percentage of participants completing all study procedures divided by total enrolled. Coded reasons for dropouts.
 - Timeframe: 3 months
2. Treatment-specific adherence rates to study protocol
 - Defined as number of phone-call check-ins attended by each participant (4 for mindfulness training, 12 for contingency management).
 - Timeframe: 3 months

6) Data and Specimen Banking*

There will be no data or specimen banking.

7) Data Management*

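### Secondary Outcome 2 scores mindfulness adherence on four short check-in calls, not on attendance at the eight group sessions, so the rate does not measure treatment received and is not comparable with the CM rate

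*Combined protocol and SAP*

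**What the plan says.** Section 5, Secondary Outcomes, item 2 concerns adherence rates by treatment over 3 months: "Defined as number of phone-call check-ins attended by each participant (4 for mindfulness training, 12 for contingency management". No other definition of adherence appears in the document.

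The Arm 1 text in section 5 describes two kinds of MT contact:

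- The treatment: "They will receive twice weekly group sessions (eight total during 4 weeks) via Zoom or in person". On length: "Each session will last 45-60 minutes".
- The call: "Participants will receive a weekly phone call to ask a few questions on their use of the mindfulness practices taught in the sessions". On length: "This will take about 5 minutes".

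Attendance at the sessions is captured elsewhere. Both the end-of-treatment and the 3-month assessment list this item: "Information on number of sessions that was attended". The Arm 1 payment schedule also includes $10 "for attending each of the 8 sessions", and section 15 repeats the per-session payment. Neither place links attendance to the adherence outcome.

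The Arm 2 text schedules CM contacts by Zoom, three a week for three weeks after the quit date. At these the participant gives a breath or saliva sample and earns the reward if abstinent. Section 7 plans a mainly descriptive feasibility analysis that compares the arms on implementation, adherence, retention and treatment perceptions.

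**The concern.** An adherence rate labelled as specific to the treatment should tell the reader how much of the treatment was taken up. In MT the counted contact is not the treatment but a short call asking about it. The eight sessions, which are what the protocol mainly asks of an MT participant, do not enter the rate.

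Two things are at stake. The MT figure may be reported as adherence when it reflects answering the telephone. And the comparison between arms would set that figure beside a CM figure that appears to count the contacts at which CM is delivered, so a difference between the two rates would have no clear meaning. The second problem would remain even if the CM count were beyond dispute.

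**Working it through.** **Inputs**

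- Adherence denominators: 4 (MT) and 12 (CM), from Secondary Outcomes, item 2.
- MT sessions: 2 a week for 4 weeks, 45 to 60 minutes each. MT calls: 1 a week, about 5 minutes each. Both from the Arm 1 text.
- MT payments: $20 baseline, $10 per session, $10 end of treatment, $25 at 3 months, total $135 (Arm 1 text).
- CM contacts: 3 a week for 3 weeks. Rewards start at $5 and rise by $2, with a $2 bonus for 4 consecutive successes (bonus total $4) and a stated maximum of $176 (Arm 2 text; section 15).

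**1. Which contact does the MT figure of 4 count?** Calls: 1 x 4 weeks = 4, which reproduces the stated denominator. Sessions: 2 x 4 weeks = 8, which does not. The outcome counts the calls.

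**2. How far can the rate depart from treatment received?**

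| Sessions attended | Calls attended | Rate as defined | Rate on sessions |
|---|---|---|---|
| 0 of 8 | 4 of 4 | 100% | 0% |
| 4 of 8 | 4 of 4 | 100% | 50% |
| 8 of 8 | 1 of 4 | 25% | 100% |
| 8 of 8 | 0 of 4 | 0% | 100% |

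**3. Share of contact time.** Calls: 4 x 5 = 20 minutes. Sessions: 8 x 45 = 360 to 8 x 60 = 480 minutes. Calls as a share of the two together: 20/(20 + 360) = 5.3% to 20/(20 + 480) = 4.0%. Adding the 60 to 90 minute orientation gives 20/440 = 4.5% to 20/590 = 3.4%.

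**4. Do calls and sessions carry the same incentive?** 20 + 8 x 10 + 10 + 25 = $135, the stated total. The sessions are paid and nothing is left over for the calls, so attendance at one need not track attendance at the other.

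**5. The CM side of the comparison.** 3 x 3 = 9 contacts, against 12 in the outcome definition. The mode differs too: Zoom in the Arm 2 text, phone in the outcome.

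- With 9 samples: 5 + 7 + ... + 21 = 117; bonus 2 x 2 = 4; sum 121. Adding assessments of 20 + 10 + 25 = 55 gives $176, the stated maximum.
- With 12 samples: 5 + 7 + ... + 27 = 192; bonus 3 x 2 = 6; sum 198. Adding 55 gives $253.

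The payment figures fit 9 contacts and the outcome definition says 12. If 9 contacts take place and the denominator stays at 12, full attendance scores at most 9/12 = 75%.

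**The case against.** The strongest reply is that MT uptake is not lost. Session attendance is recorded twice and must be known for payment. Retention is a separate secondary outcome, with coded reasons for dropout. Three acceptability items and post-intervention interviews are planned, and section 7 names implementation apart from adherence, so attendance could be reported there. All of this stands. A reader might infer from the call-based definition that MT feasibility goes unmeasured, and the documents do not support that. What remains is that attendance is never named as an outcome, the implementation measures are not defined, and retention is the share of enrolled participants who finish every procedure, which gives no session count per person.

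A second reply is that the outcome is labelled as adherence to the study protocol, and the calls are a protocol procedure. The arm-specific wording may only mean that results are given by arm, as it seems to for retention. That reading is possible. It does not explain why the main protocol activity in MT is left out.

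Third, the extreme rows of the table are logical limits; nothing in the plan says they are likely. Nor does share of contact time prove that calls are a poor proxy. Both are fair. The table shows what the definition permits, not what is expected.

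Fourth, that the counted CM check-ins are the treatment contacts is an inference, since neither number nor mode matches the Arm 2 text. This limits how firmly the between-arm point can be put.

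**Conclusion.** The point holds for the definition. As written, the MT adherence rate counts 4 brief calls, omits the 8 sessions, and can lie anywhere from 0% to 100% whatever the session attendance. The calls are about 4 to 5% of combined call and session time. The planned between-arm comparison of adherence is not like with like, on the reading that the CM check-ins are the contacts at which samples are given and rewarded.

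Assumptions: the weekly calls run over the 4 treatment weeks (which reproduces the stated 4), and the fractions refer to one course of each intervention.

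A reader might also infer that a decision to take MT forward would rest on this number. The documents do not support that. They state no progression criterion, the outcome is secondary with a mainly descriptive analysis, and attendance, retention, acceptability and abstinence would all be to hand. Feasibility is an aim in the Background; the Objectives section names only the best strategy for confirmed abstinence. The defect is worth correcting because uptake of MT is a central result for a pilot that proposes to test MT feasibility, but it does not touch the primary outcome.

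**What to change.** In section 5, Secondary Outcomes, item 2:

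- Define MT adherence as the number and proportion of the 8 group sessions attended.
- Report completion of the weekly calls separately, as a process measure.
- Reconcile the 12 phone check-ins with the 9 Zoom contacts in the Arm 2 text and with the payment figures there and in section 15. Then define CM adherence as the proportion of scheduled CM contacts attended with a sample provided.
- In section 7, state that the arms are compared descriptively on these proportions.
- Say whether the rate covers the Stage 1 intervention only or also the one received after a Stage 2 switch; the current text is silent.

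Cost: a protocol amendment that redefines one secondary outcome in both arms, preferably dated before adherence is compared between arms. MT needs no new data collection, since attendance is already recorded at both follow-ups and tied to payment. In CM, the reward schedule already depends on a result at each contact.

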3) Inclusion and Exclusion Criteria***A. Inclusion Criteria**

To be eligible participants should:

- Diagnosed with HIV (based on self-report).
- Be 18 years and older
- Have smoked ≥ 5 cigarettes/day in the past year

- Be interested in making a quit attempt in the next 30 days
- Own a smartphone (apple/android), and plan to keep it active for the next 6 months
- Able to consent
- Have no plans to move in the next 6 months
- Are not pregnant or planning to be pregnant in the following 6 months
- Have any condition that, in the opinion of the investigator, would compromise the well-being of the patient or the study or prevent the patient from meeting or performing study requirements

B. Exclusion Criteria

Participants would be excluded if they:

- Have contraindication to NRT (past month myocardial infarction, history of serious arrhythmias/or unstable angina pectoris, dermatological disorder)
- Are currently being treated for a psychiatric condition.
- Are currently being treated for smoking cessation, alcoholism, or illicit drug use
- Are adults unable to consent
- Are individuals who are not yet adults
- Are pregnant women
- Are prisoners

4) Study Design

- a. Study Type – Interventional
- b. Primary Purpose – Other
- c. Interventional Study Model – Sequential
- d. Number of Arms – 2
- e. Randomized or not – Randomized
- f. Open label or if blinded – Not blinded
- g. Number of participants – 100

5) Procedures Involved*

We will recruit participants via community and clinic flyers and among participants of another on-going survey who smoke (IRB#20180269). In Stage 1, participants will be randomized into one of two groups: 1) a group mindfulness training (MT) for smoking cessation, or 2) contingency management (CM) for smoking cessation. In Stage 2 non-

responders (those who have not quit at 1 month evaluation) will be randomized to: 1) *Switch* to sequentially receive the other intervention (i.e., CM or MI) and complete the 3-month assessment; or 2) *Continue* without further intervention and complete the 3-month assessment only.

In stage 1, both groups will do the following:

- Complete a baseline survey.
- Receive 6 weeks of Nicotine Replacement Treatment (NRT) via mail
- Receive reminder/encouragement calls or texts the day before their quit date and 2 weeks after their quit date.

Arm 1: The MT smoking cessation intervention:

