Participants in this arm will attend an orientation session via Zoom that will last 60-90 minutes. They will connect with a research associate 3 times per week for 3 weeks after quit date via zoom where they will answer a few questions about their quitting progress, report on past 7-day smoking, and provide a sample of CO to verify their smoking status after their quit date using a portable CO monitor (coVita iCO™ Smokerlyzers®) and/or NicoTests saliva screen test that has been mailed to them. Those who proved their abstinence (CO< 8 ppm using coVita iCO™ Smokerlyzers®) and/or 30 ng/mL using NicAlert) [14] will receive a cash reward. The first successful CO sample earns \$5 cash, and then the reward increases by \$2 for each consecutive successful CO and/or saliva sample (e.g., \$5, \$7, \$9...). Participants also earn \$2 bonus for 4 consecutive successful CO and/or saliva samples (total=\$4). In all, participants can earn a maximum of \$176. Participant who fail the CO and/or saliva test will not receive reinforcement and the value of the next payment will be reset to the one that was missed.

Figure (1): overview of the study design

All participants will be asked to complete an end of treatment assessment 2 weeks after the intervention ends, which will be the same as the 3-month follow-up described below. Breath CO and/or saliva sample test (for cotinine analysis) will be collected at the end of treatment assessment via Zoom for participants who report they have quit.

All participants will be asked to complete a follow-up assessment 3 months after their quit date to assess their smoking status as well as get information about concomitant smoking and NRT use, use of additional NRT or cessation drugs (e.g., bupropion), and use of other tobacco methods. Breath CO and/or saliva sample test (for cotinine analysis) will be collected at the 3-month follow-up points for participants who report abstinence. The breath sample will be collected with the portable CO monitor (coVita iCO™ Smokerlyzers®) and/or NicoTests saliva screening test. A cut-off of 8 ppm for CO test (using coVita iCO™ Smokerlyzers®) and/or ≤ 30 ng/mL for the saliva sample test (using NicoTests) will be used to determine abstinence (Benowitz et al 2002).

Study measures

1. Baseline Assessment: All study materials and instrument will be translated into Spanish.

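### The adherence outcome lists 12 contingency management check-ins, but the protocol schedules only 9 contacts

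*Combined protocol and SAP*

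**What the plan says.** Under Secondary Outcomes, item 2 is headed as treatment-specific adherence rates. It is defined as the number of phone-call check-ins each participant attends, "4 for mindfulness training, 12 for contingency management", over a 3-month timeframe. No formula for a rate is given.

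Section 5, Arm 2, sets the CM contact schedule: participants meet a research associate "3 times per week for 3 weeks after quit date via zoom". Each contact includes a few questions, a report of recent smoking and a breath or saliva sample. The first successful sample earns 5 dollars, and each consecutive success earns 2 dollars more than the last. There is a 2-dollar "bonus for 4 consecutive successful CO and/or saliva samples", with a stated bonus total of 4 dollars. The stated maximum is 176 dollars.

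Section 15 (Recruitment Methods) repeats these terms, describes the 176 dollars as rewards, and lists assessment payments of 20, 10 and 25 dollars.

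Section 5, Arm 1, gives MT participants a weekly phone call alongside a four-week course, and a payment total of 135 dollars.

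Section 7 (Data Management) says that adherence will be compared between arms 1 and 2, in an analysis of feasibility and acceptability that is largely descriptive.

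**The concern.** The two CM figures cannot both describe the same contacts: the schedule gives 9 and the outcome gives 12. The MT figure of 4 does agree with its schedule, so the mismatch affects one arm only.

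The outcome is called a rate, and 4 and 12 are the only candidate denominators in the protocol. An analyst who follows the text would divide CM attendance by a number of contacts that were never scheduled. CM adherence would look worse than it is, MT adherence would not, and the between-arm comparison in section 7 would carry the difference.

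The wording adds uncertainty about what to count. The outcome speaks of phone calls, while the scheduled CM contacts take place on Zoom.

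**Working it through.** **1. Scheduled contacts**

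- CM (section 5, Arm 2): 3 per week x 3 weeks = 9. Reaching 12 would need 3 per week x 4 weeks.
- MT (section 5, Arm 1): 1 call per week x 4 weeks = 4, taking the calls to run for the length of the course. This matches the listed 4.

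**2. The plan's payment totals**

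The MT total shows how the protocol builds such a figure: 20 (baseline) + 8 x 10 (sessions) + 10 (end of treatment) + 25 (3 months) = 135 dollars, as stated. It includes the assessment payments.

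For CM, n consecutive successes earn 5 + 7 + 9 + ... = n(n + 4) dollars. The bonus is 2 dollars for each completed block of four. The assessments add 20 + 10 + 25 = 55 dollars.

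| Paid samples n | n(n + 4) | Bonus | Rewards | Rewards + 55 |
|---|---|---|---|---|
| 8 | 96 | 4 | 100 | 155 |
| 9 | 117 | 4 | 121 | **176** |
| 10 | 140 | 4 | 144 | 199 |
| 11 | 165 | 4 | 169 | 224 |
| 12 | 192 | 6 | 198 | 253 |

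- The 4-dollar bonus total holds for n = 8 to 11. Twelve samples would give 6 dollars.
- The 176-dollar maximum is reproduced exactly at n = 9 when assessments are included, as they are in the MT total.
- Read as rewards alone, 176 dollars fits no n: the figure passes from 169 at n = 11 to 198 at n = 12.

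**3. Effect on the adherence rate**

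Suppose 9 contacts are delivered and 12 is the divisor.

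- Full CM attendance: 9/12 = 75%. Full MT attendance: 4/4 = 100%.
- Every CM rate is multiplied by 9/12 = 0.75. For example, 6 contacts attended would be 6/9 = 67% on the scheduled number but 6/12 = 50% on the listed one.
- If raw counts are reported, 12 does not enter and nothing is distorted.

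**The case against.** The best defence is that the outcome is defined as a count. The heading mentions rates, but no division is specified, so the 75% figure arises only if 12 is used as a divisor. This stands. It limits the harm without explaining the mismatch.

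A second defence is that the pair 4 and 12 is coherent over four weeks: weekly MT calls give 4 and thrice-weekly CM contacts give 12. The primary outcome has a four-week time point. The sponsor may therefore intend a fourth CM week. But the Arm 2 text says three weeks, and the 4-dollar bonus total does not fit 12 paid samples. One of the two statements needs correcting either way.

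A reader might also bridge the gap by adding the CM orientation and the two reminders, since 9 + 1 + 2 = 12. The protocol does not define check-ins that way. The reminders, "Receive reminder/encouragement calls or texts the day before their quit date and 2 weeks after their quit date", may be texts, which nobody attends. MT participants have an orientation and the same reminders, yet their figure is 4.

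In the other direction, a reader might infer that the payments prove there are 9 check-ins. They do not. Payments concern paid samples, and the match to 176 dollars needs the total-compensation reading, while section 15 calls the sum rewards and lists assessment payments separately. The schedule mismatch carries the point and the payments only support it.

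Two further inferences also go too far. One is that the figures fail for Stage 2 participants who switch intervention. The numbers are given per treatment, so each can be applied to the treatment received. The other is that check-in attendance may go unrecorded. Section 7 has all study data captured in REDCap, and each CM contact yields answers and a sample that decides a payment, so attendance would ordinarily follow from those records.

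**Conclusion.** The point holds as a minor error. The adherence outcome lists 12 CM check-ins, the protocol schedules 9 CM contacts, and no text accounts for the remaining three. The bonus total argues against 12 paid samples, and the maximum payment agrees with 9 on its more likely reading.

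The size is conditional. If 9 contacts are delivered and 12 is the divisor, CM adherence is scaled to three quarters of its true value and MT adherence is not. At full attendance that is 75% against 100%.

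A reader might infer that the trial's adherence comparison is certain to be biased, or that its efficacy results are affected. The documents support neither. No rate formula is given, raw counts would be undistorted, the analysis is descriptive, and the abstinence outcome does not use this number.

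**What to change.** - In Secondary Outcomes, item 2, change 12 to 9.
- If a fourth week of CM contacts is intended, correct section 5, Arm 2, and section 15 instead: the schedule becomes four weeks, the bonus total 6 dollars, and the maximum 253 dollars with assessments (198 in rewards alone).
- Describe the CM check-ins as the scheduled Zoom contacts, and keep phone calls for MT.
- Define the rate as contacts attended divided by contacts scheduled, separately for each treatment.

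With 9, the cost is one number and one definition, which can be settled before analysis without any change in conduct. With a fourth week, there are three more contacts per CM participant and up to 253 - 176 = 77 dollars more in payments, taking 176 as total compensation.
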